### **Phase I. Open trial and RCT**

**Study overview.** In this treatment development grant, 70 adolescents in Probation will be recruited to participate in the study. The first 10 will participate in an iterative development open trial. Then 60 youth will be randomized to: 1) the screening/brief intervention safety planning intervention, or 2) standard practice.

**Open Trial Design.** A total of 10 youth will be recruited for open trial in order to: a) test the protocol's applicability in Probation, and b) train the mental health counselors in the protocol. We have used this 2 phase approach extensively in prior studies. The open trial will occur in months 5 - 8 after counselor training. The protocol and procedures will be modified as necessary after the first 5 participants and then again after 10 pilots have been run through the protocol and prior to conducting the pilot RCT

[figure not shown]
**Overview of RCT Trial Procedures.** When youth arrive for their first Probation appointment, they are asked to complete the MAYSI/NSSI assessment. Youth who flag in on the MAYSI or NSSI item on this first screen, will be referred by their PO to the mental health counselor who will approach them about participation in the study. If the parent/caregiver consents to the study, the mental health counselor will then meet with the youth, physically separate from the parent/caregiver, to describe study procedures in detail (**including the fact that only youth who are positive on the secondary screen continue in the study**) and obtain juvenile assent without parental presence (see **Human Subjects**). Consenting procedures will also include permission to access court records. All youth will then complete the complete the Self-Injurious Thoughts and Behaviors Interview 2.0 (SITBI-Short Form^91, see below), to more thoroughly assess self-injurious behavior. Families will then be referred back to their PO to complete the secondary screen. If the youth screens in, he/she is then randomized to either standard practice or the safety planning intervention.

Follow-up assessments will also be completed at 1- and 3-months post-baseline to gather data on youth outcomes related to treatment, self-harm, and recidivism. No juvenile will ever be sanctioned by the court for not agreeing or being unable to participate in the research study (see **Human Subjects/Letter of Support**).

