representation will be about 22% Africa American or Black (and other) and 72% White. **Estimated Sample Size and Retention Rates.** In 2016, the RIFC handled offenses for 2,634 juveniles of whom 764 (29%) were female and 2,581 (98%) who were in the 12-17 year old age range. The Juvenile Intake Department, for example, screens more than 904 juveniles per year and, of those youth who are screened, approximately 10% (N=89) flag for recent SI. In 2015, the detention center admitted 470 youth. *Probation had a caseload of 375 in 2015. Of these youth, it is estimated that 20% of youth screen positive for current risk of self-injurious behavior (N=75). Even with a conservative acceptance rate of 60%, we would be able to recruit about 45 youth per year and meet our 20 month projected enrollment goal of 60 participants, i.e. about 3 per month (3 x 20 = 60). Using a conservative follow-up rate of 80% (see **Retention**) of the 60 enrolled and retained participants, approximately 48 are expected to complete the 3-month follow-up.* This approach is feasible given our excellent working relationship with the JJS, including the RIFC, and prior experience recruiting from the juvenile intake department (see RIFC Chief Judge and Probation Letters of Support). MPI [name] collaborated on a 24-month longitudinal epidemiological study of first-time CINI offenders at the RIFC and we successfully recruited the entire sample of 400 first-time offending CINI youth (DA034538). MPI [name] is also currently recruiting at the RIFC juvenile intake department for a baseline sample of suicidal CINI youth for her NIMH K23 Mentored Career Award. MPI [name] also successfully established a referral system from RIFC to his NIAAA (AA017659) and NIDA (DA0029871) trials for youth with substance use-related court involvement.

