#### **Background variables (obtained at baseline only).**

Standard demographic variables including age, sex, race, ethnicity, and education will be recorded from court records. (note: at the follow-up, youth will be asked questions about their gender identity because it is not currently asked in Probation). Legal history will also be obtained (available to study staff) as will item-level responses for the MAYSI-2 and NSSI screening data. The collection of data from legal records and existing JJS procedures is an additional strength of this service-based application as it improves feasibility and the potential for scalability.

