#### **Youth level outcomes**

Feasibility of a future larger trial, will be defined as the percent of at-risk youth who enroll in the research project. Feasibility of conducting safety planning in Probation will be assessed by the percentage who receive the brief intervention, including linkage to treatment and the follow-up phone call, in total and in part.

Acceptability will be assessed by post-intervention ratings on the Client Satisfaction Questionnaire [CSQ-8;120], a well-established 8-item self-report instrument on a 4-point scale used to assess patients' satisfaction with psychiatric treatment. A score above 24 is the benchmark based on previous research. An "exit interview" will also be conducted at the one month follow-up about the intervention protocol that they received.

The Self-Injurious Thoughts and Behaviors Interview 2.0 (SITBI 2.0) Short Form^91 is a structured interview designed to assess the presence, frequency, and characteristics of a broad array of self-injurious thoughts and behaviors. The SITBI has good reliability and validity. The SITBI will be completed at baseline and 1 and 3-month follow-up to assess suicidal ideation, attempts, and NSSI. Suicidal events will be operationalized as a composite score of suicide attempts and emergency interventions for acute suicidality assessed by the CASA (see below). Recidivism (collateral data from RIFC database) including new arrests, description of related charges (e.g., substance-related, property) and time detained/incarcerated (all tracked by the RIFC database) will be available.

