### **Phase I: Data Analysis Plan**

Prior to conducting analyses for the project aims, a series of routine procedures will be conducted to ensure the data accuracy/adequacy. All forms will be checked for missing data and all data will be double entered and backed-up daily. Descriptive statistics will be examined for distributional properties of the variables (e.g., normality, internal consistency). The data will be transformed to achieve normality if needed.

We will conduct analyses in an intent-to-treat (as randomized) manner, and examine as primary analyses unadjusted and secondarily adjusted for selected covariates identified above. Masking integrity will be reviewed. ANCOVA (outcome regressed on baseline) methods will be used, and linear mixed effect models will be used to account for non-independence of repeatedly observed outcomes.

We will examine attrition by comparing follow-up assessment completers and non-completers on socio-demographic and baseline data to determine if they differ systematically. Consistent with an intent-to-treat model, we will include all randomized participants in the analyses. Attrition/Missing Data. It is anticipated that less than 20% of subjects will not have follow-up data. We will test for differential attrition across the experimental condition and the baseline comparison. The analyses described below can account for attrition at the follow-up points. We will employ multiple imputation as our primary approach to missing data [138] and will conduct a sensitivity analysis treating all participants lost to follow-up as treatment failures at the point of loss, i.e. assuming no change on their self-injury-related mechanisms or outcomes. If our primary conclusions are similar with and without extreme missing data assumptions, confidence in the findings will be higher.

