**Primary Aim.** Our primary aim is to examine feasibility and acceptability of the safety planning intervention to inform next-step study design. **Feasibility** of a larger future trial will be evaluated based on: a) enrollment rates for the research project (target = 70%), and feasibility of the intervention, b) the percentage of participants who complete the entire intervention protocol (target = 70%). We will also determine the appropriateness of our assessment battery for a larger, future trial, by examining whether the range of responses to instruments indicate sufficient variability and change over time. **Acceptability** will be demonstrated by study withdrawal (< 20%) and > 80% of the responses on a consumer satisfaction scale rated as highly satisfactory. We will use logistic regression to model binary outcomes of enrollment, completion of the protocol, and withdrawal as a function of treatment assignment. We will use ordinal logistic regression for the satisfaction scale analysis.

With respect to youth level clinical outcomes, the goal is to obtain a reasonably precise estimate of the standard deviation for the outcome variables, and pre-post correlations of outcome variables, which are essential statistics for powering a definitive trial. Following Leon et al (2011) and Kraemer et al (2006), our goal is not to obtain a preliminary estimate of the treatment effect size, but as per Teare and colleagues (2014), the size of the pilot we propose is sufficient to obtain sufficiently precise estimates of key variance and covariance parameters necessary to design a definitive trial. Our approach will be to conduct an analysis consistent with the testing of the hypothesis that JJS youth enrolled in the experimental condition have less self-injurious ideation and behavior at 1 and 3 month follow-up relative to youth enrolled in standard practice. We will also examine mechanisms including treatment attendance, safety skill acquisition, motivation for

treatment, and treatment barrier reduction. The main outcomes are suicidal ideation and suicide attempts/NSSI on the SITBI.

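### The plan does not consistently put baseline SITBI in the main model for continuous SITBI scores, and its detectable d = .62 does not match the 60 youth randomized

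*Combined protocol and SAP*

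**What the plan says.** Three places bear on the main model.

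- The opening of Phase I: Data Analysis Plan will "examine as primary analyses unadjusted and secondarily adjusted for selected covariates identified above". Shortly afterwards it says "ANCOVA (outcome regressed on baseline) methods will be used", with no rank.
- The mixed-model paragraph under Primary Aim regresses the 1- and 3-month outcomes on treatment and a time-by-treatment interaction. Its main inference comes from a treatment test pooled over the two visits. Covarying baseline SITBI appears there as a further set of analyses.
- The Power paragraph gives d = .62 as the square root of 16 × (1 − .8²)/15. It cites a reliability of .8 and an autocorrelation of .64, and puts 70 participants in the RCT.

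The baseline score is available in time. Under Overview of RCT Trial Procedures, "All youth will then complete the complete the Self-Injurious Thoughts and Behaviors Interview 2.0"; the secondary screen follows, and "If the youth screens in, he/she is then randomized to either standard practice or the safety planning intervention". Youth level outcomes confirms the schedule: "The SITBI will be completed at baseline and 1 and 3-month follow-up to assess suicidal ideation, attempts, and NSSI".

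**The concern.** A pre-randomization measure of the same construct is usually the most useful covariate a small trial has. Here it costs no extra data, yet the text does not firmly place it in the model from which the main inference is drawn. If the unadjusted version leads, the headline clinical comparison is the less precise of two analyses already planned. If the adjusted version was meant to lead, the plan does not say so.

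The power statement does not settle the matter. Its (1 − r²) factor has the form of a baseline-adjusted variance, which sits awkwardly with a primary analysis described as unadjusted. Its 15 per group matches no sample size in the protocol.

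**Working it through.** **Inputs from the documents.** There are 60 youth randomized, and "approximately 48 are expected to complete the 3-month follow-up". The Power paragraph gives an autocorrelation of .64, used here as the correlation between the 1- and 3-month scores.

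**Assumptions.** Allocation is 1:1, so 30 per arm randomized or 24 per arm followed. Power is 80% at two-sided 5%, which is what the constant 16 in Lehr's formula represents. The outcome is continuous with equal variance at each visit. The baseline score has the same correlation ρ with both follow-ups. The documents do not give ρ, so .3, .5 and .64 are used as a range.

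**The plan's own figure.** √(16 × (1 − .8²)/15) = √(5.76/15) = .62, so it reproduces as printed.

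- Without the factor, 15 per group gives √(16/15) = 1.03, close to the d = 1.0 stated for the t-test.
- With the factor kept and 30 per group, the result is √(5.76/30) = .44.
- The factor does not show which correlation is meant, because .8² equals the quoted autocorrelation of .64. An ANCOVA with a correlation of .64 would use 1 − .64² = .5904, giving .79 at 15 per group and .56 at 30.
- The 70 in the Power paragraph equals the 10 open-trial youth plus the 60 randomized. The opening description, the study overview and the sample-size paragraph all randomize 60.

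**Pooled contrast, in units of the single-visit variance.**

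- Unadjusted: v = (1 + .64)/2 = .82.
- Adjusted for baseline: v = .82 − ρ².
- Cost of estimating one slope: a factor of 1 + 1/(N − 4), which is 1.018 at N = 60 and 1.023 at N = 48.
- Detectable d = √(16 × v × cost factor/n), with no cost factor for the unadjusted analysis.

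| ρ (assumed) | v | Net variance cut, 30 per arm | d, 30 per arm | d, 24 per arm |
|---|---|---|---|---|
| unadjusted | .82 | – | .66 | .74 |
| .3 | .73 | 9% | .63 | .71 |
| .5 | .57 | 29% | .56 | .62 |
| .64 | .41 | 49% | .47 | .53 |

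For example, at ρ = .5 and 30 per arm, .57 × 1.018 = .580. The net cut is 1 − .580/.82 = 29%, and d = √(16 × .580/30) = .56. By the noncentral t, power at d = .5 with 30 per arm moves from 56% to 60%, 71% or 84%.

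**Downside.** At ρ = 0 adjustment adds 1.8% to the variance at 30 per arm and 2.3% at 24 per arm. It breaks even at ρ = √(.82 × (1 − 1/1.018)) = .12 at 30 per arm, and at .14 at 24 per arm.

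**Checks.** A simulation of 20,000 trials at 24 per arm with ρ = .64 found both estimators unbiased, with standard errors .262 and .187 (variance ratio .51). If the follow-up correlation is .5 instead of .64, the net cuts at 30 per arm are 10%, 32% and 54%. If it is .8, they are 8%, 27% and 45%.

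**Where the gain does not carry over.** With 30 per arm, a yes/no outcome and a yes/no baseline (assumed rates 30% v 10% and 50% v 25%), adjustment changed simulated power by −1 to +2 points at a latent correlation of .3 and by +5 to +9 at .64. The log odds ratio itself moved 3–4% or 16–24% away from zero, because the conditional odds ratio is a different quantity. With rates of 10% v 3%, at least one arm has no events in 1 − (1 − .97³⁰)(1 − .90³⁰) = 43% of trials.

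**The case against.** The strongest reply is that the plan may already intend what is asked. The primary/secondary sentence ranks adjustment for selected covariates and does not mention baseline SITBI. The ANCOVA sentence is flat, and the (1 − r²) factor in the Power paragraph is compatible with baseline adjustment. On that reading, ANCOVA is the working method and unadjusted means without further covariates. This stands to the extent that a reader who infers a settled decision to rank baseline SITBI second goes beyond the text. It is the likelier reading only because the model paragraph omits baseline from the model it describes and adds it as a further analysis. The same rewording resolves either reading.

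Second, this is a pilot. The Primary Aim paragraphs say "our goal is not to obtain a preliminary estimate of the treatment effect size", and standard deviations and pre-post correlations can be estimated whichever model leads. That limits the stakes but does not remove the point, because the plan still tests hypotheses and names a main inference.

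Third, the gain rests on a correlation that the pilot is itself meant to estimate, and at .3 it is small. This also stands. The argument for adjusting is the imbalance between a loss of about 2% at worst and a possibly large gain.

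Fourth, the scope is narrow. The documents define no continuous SITBI score, so the point reaches only those SITBI outcomes that are analysed as continuous scores.

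A reader might also infer that the unadjusted test is biased, or that the model is misspecified because no separate time term is listed. Neither is supported. Randomization makes the unadjusted comparison valid, and nothing is lost if time is treated as categorical.

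**Conclusion.** The point holds as a matter of clarity and efficiency, not validity. For continuous SITBI scores the plan does not fix whether the main model contains the baseline score, and its likelier reading leads with the less precise analysis. Under the stated assumptions, the precision forgone ranges from minor (ρ = .3) to about half the variance (ρ = .64). No decision on the feasibility and acceptability aim depends on it.

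The d = .62 needs restating under either reading. It rests on 15 per group, which is not the trial's size, and on a correlation whose role is unclear. An unadjusted pooled analysis at 35 per arm would give √(16 × .82/35) = .61. A reader might infer from this that the printed figure is right for 70 youth. The printed formula is not that calculation, and 70 includes the open-trial participants.

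**What to change.** For continuous SITBI outcomes, state one main model: the 1- and 3-month scores on treatment, categorical time, treatment-by-time and the baseline SITBI score for the same construct. Base the main inference on the treatment contrast averaged over both visits, and report the unadjusted comparison as supportive. Say that the ANCOVA sentence refers to this model. For binary or rare attempt and NSSI outcomes, keep adjustment supportive.

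In the Power paragraph, reconcile 70 with 60, give the actual number per arm, say which correlation is used and for what, and match the formula to the chosen model. The table above gives the values for unadjusted and adjusted pooled analyses. Label any baseline-to-follow-up correlation as assumed and show a range.

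The cost is a few sentences in the analysis plan. No visit, measure or participant burden is added, and the statistical price is one estimated slope.

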COVER PAGE

Date: 2-25-20

Study Protocol

: NCT03655470

Brief Title: Safety Planning in Juvenile Justice for Suicidal Youth

Official Title: Screening and Brief Intervention for Suicidality and Nonsuicidal Self-Injury Among Youth in the Juvenile Justice System

Secondary IDs: 1R34MH114307-01A1 [U.S. NIH Grant/Contract Award Number]

The proposed study will be divided into two phases. In Phase I, we will conduct an open trial with 10 adolescents which will allow us to make any modifications necessary for using the protocol in Probation. We will then randomize 60 suicidal JJ youth who screen positive for recent SI into standard care or the safety planning intervention. We will train two part-time counselors who have a master's degree in the mental health field and work in the local community mental health clinic, Gateway, in which MPI [name] and Co-I [name] have consulted. Counselors with community mental health experience were selected because youth in the JJS are typically served by community mental health clinics, so this choice was also made with an eye toward eventual implementation. In addition, the model proposed here – of mental health counselors embedded in Probation – is consistent with a co-responder model, found across the U.S. in which a PO works collaboratively with a mental health professional to coordinate care. Thus, if the protocol is found to be effective, there is an existing infrastructure that could aid further implementation. We will hire a bilingual counselors so they will be able to conduct the intervention and give feedback to youth and parents who are Spanish-speaking.

The counselors will cover afternoon appointments in Probation and be employed by the research grant because Probation rules prohibit audiotaping sessions with youth. By employing the mental health counselors on the grant, we will be able to rate tapes of sessions for fidelity and competency (see below). In order to conduct the study under conditions most relevant to a future implementation trial, we will also employ a training approach that has been successfully implemented by Co-I [name] with Bachelors and Masters level staff in a psychiatric hospital (see below)..

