**Current standard practice.** The MAYSI-2 provides two cut-off scores: caution (2 items endorsed) and warning (3 or more items endorsed). (Note: a screening item from the SITBI – “Have you ever had thoughts of purposely hurting yourself without wanting to die, e.g. cutting, burning? If yes, how many separate times in your life?” – has also just been added as part of standard practice). If a teen has a positive screen for suicide risk, the PO completes a “secondary screener” built into the MAYSI- 2 to determine whether there is concern of current and/or imminent risk. If a teen endorses NSSI more than once in the prior year, then the PO asks about frequency and severity. If there is ongoing concern of risk for self-injurious behavior, then the PO arranges for a crisis evaluation in the Emergency Department (ED). If the teen is not judged to be at imminent risk, the PO makes a referral back to the current treatment provider or to a community mental health clinic. In either case, the parents and youth receive a packet with mental health resources.

In the experimental condition, if a teen screens positive on the secondary screener, and is randomized to

*the safety planning intervention, the PO will refer the case to the mental health counselor. The mental health counselor will conduct the safety planning intervention (described below) and then make a decision whether*

*the teen remains at imminent risk, and needs to be referred for an ED evaluation. If there is no imminent risk, the PO and mental health counselor together facilitate a referral back to the current treatment provider or to a community mental health clinic. The mental health counselor will also conduct a follow-up phone call one week after the safety plan to answer any questions about the safety plan and promote linkage to treatment as needed.*

**Participants.** Youth offenders, ages 12-17 will be eligible for enrollment with the following criteria: 1) Legal guardian available to consent for juvenile's participation, 2) Juvenile and parents are English or Spanish speaking; and 3) Juvenile flags in on the MAYSI-2 or NSSI item. *In order to maximize the ecological validity of this pilot trial, there will not be any exclusion criteria.* **Racial and Ethnic Minority**

**Considerations.** Consistent with 2016 RIFC statistics, ethnic representation will be approximately 18% Hispanic and racial

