We will use generalized linear mixed models to test hypotheses that participants randomized to the safety plan condition will have significantly improved outcomes compared with those who receive standard practice. This approach accommodates varying numbers of observations across individuals (allowing the inclusion of all randomized participants) while controlling for within-subject correlation. Scores from continuous measures are the dependent variables and treatment condition is the primary independent variable. Analyses will also be conducted co-varying baseline SITBI scores. These hypotheses will be evaluated by regressing the outcome variables as observed on the 1 and 3-month follow-ups on treatment condition, and a time by treatment condition interaction in a general linear mixed effect modeling framework. Main inferences will be based on post-hoc omnibus tests of treatment group effects pooled over time points, and secondary inferences will be drawn from the time-specific outcomes.

The current study also seeks to illuminate factors that may better guide treatment decision making by identifying those who are most likely to benefit from the proposed interventions. Specifically, in exploratory analyses, we will examine sex, race, and ethnicity to address the barrier of racial disparities.

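### For suicide attempts/NSSI, the single no-change sensitivity analysis is a moderate scenario, not an extreme one, so its agreement with multiple imputation does not show robustness to harsher outcomes in lost safety-planning youth

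*Combined protocol and SAP*

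**What the plan says.** All references are to the combined protocol and SAP.

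- **Phase I: Data Analysis Plan, Attrition/Missing Data.** Multiple imputation is the primary approach. The one sensitivity analysis is "treating all participants lost to follow-up as treatment failures at the point of loss, i.e. assuming no change on their self-injury-related mechanisms or outcomes". The next sentence gives its use: "If our primary conclusions are similar with and without extreme missing data assumptions, confidence in the findings will be higher". Completers are compared with non-completers, and differential attrition is tested, but neither step varies the outcomes assumed for the lost.
- **Primary Aim.** Feasibility and acceptability are primary, and obtaining a preliminary effect size is disclaimed as a goal. On the clinical side, "The main outcomes are suicidal ideation and suicide attempts/NSSI on the SITBI".
- **Entry.** The opening summary says the trial will "randomize 60 suicidal JJ youth who screen positive for recent SI into standard care or the safety planning intervention". Under Participants, the third criterion is "Juvenile flags in on the MAYSI-2 or NSSI item".
- **Measurement.** The SITBI is "designed to assess the presence, frequency, and characteristics of a broad array of self-injurious thoughts and behaviors" and is given at baseline, 1 month and 3 months. The plan states neither its recall window nor how attempts/NSSI will be scored. The model description says "Scores from continuous measures are the dependent variables and treatment condition is the primary independent variable".
- **CASA.** "Suicidal events will be operationalized as a composite score of suicide attempts and emergency interventions for acute suicidality assessed by the CASA". Youth level mechanisms describes the CASA as a follow-up measure.

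**The concern.** For ideation, holding a lost youth unchanged is reasonably pessimistic when the baseline value is held, because youth enter after a positive screen. For attempts/NSSI it depends on history. Entry can rest on ideation alone, so some youth will have no earlier attempt or NSSI. No change scores such a youth as event-free, or as zero if frequency is used, although the same sentence calls the youth a treatment failure. Others, including some who enter through the NSSI item, may carry an earlier event forward. The plan gives no coding rule that settles the conflict.

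What is at stake is the robustness statement. The plan says in advance that agreement with an extreme assumption raises confidence. If the assumption is only moderate for a main clinical outcome, agreement says little about whether lost safety-planning youth did badly.

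A smaller gap concerns CASA-based items. A youth lost before the 1-month visit has no earlier CASA value to hold. The SITBI part of the composite and provider-reported attendance may still be available.

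**Working it through.** **Plan's own figure.** Estimated Sample Size and Retention Rates gives 60 randomized and 80% follow-up: 60 x 0.80 = 48 completers, as stated, so 12 are lost. The Power paragraph says 70 in the RCT; I use the 60 stated elsewhere.

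**Assumptions.** There are 30 youth per arm (no ratio is stated) and any-event coding. The documents give no event rates, so all rates are illustrative. Multiple imputation is approximated by giving lost youth their own arm's completer rate. Differences are safety planning minus standard practice, so negative favours safety planning.

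**General formula.** Let fS and fC be the shares lost, pS and pC the completer event rates, and b the share of the lost with an earlier event, taken as equal in the two arms.

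No-change difference = [(1 - fS)pS + fS b] - [(1 - fC)pC + fC b]

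**Equal loss (fS = fC = f).** The terms in b cancel and leave (1 - f)(pS - pC).

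- With 6 of 30 lost per arm, f = 0.20 and the factor is 0.80. With 2 of 30, close to the 94% three-month retention cited under Protection against Attrition, it is 0.933.
- Setting b = 1, an event in every lost youth, gives the same difference.
- Giving lost safety-planning youth the standard-practice completer rate also gives it: (1 - f)pS + f pC - pC = (1 - f)(pS - pC). For the comparison, the rule is therefore a no-benefit scenario for the lost.

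Illustration with completer rates 15% vs 30%, 6 lost per arm and no earlier events in the lost:

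| Assumption for the lost | Safety planning | Standard practice | Difference (points) |
|---|---|---|---|
| Own arm's completer rate | 15% | 30% | -15 |
| No change | 12% | 24% | -12 |
| Event in all lost, both arms | 32% | 44% | -12 |
| Event in lost safety-planning youth; others as completers | 32% | 30% | +2 |
| Event in lost safety-planning youth; others event-free | 32% | 24% | +8 |

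The last two rows become +8 and +12 at 10% vs 20%, and -4 and +4 at 20% vs 40%. With 2 lost per arm at 15% vs 30%, no change gives -14.0 and those two rows give -9.3 and -7.3, so nothing reverses.

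**Where no change sits on a delta scale (15% vs 30%, f = 0.20).** Shifting the imputed odds in the safety-planning arm only, by odds ratios of 1, 2, 5 and 10, gives -15.0, -12.8, -8.6 and -5.2; an event in all of them gives +2.0. The -12 from no change corresponds to imputing 30% in that arm: (0.30/0.70)/(0.15/0.85) = 2.4. Shifting both arms together gives -15.0, -16.0, -16.3 and -15.5, and -12.0 if all have events.

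**Unequal loss (12 lost, completer rates 1/6 vs 1/3; imputation gives -16.7 throughout).**

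| Lost: safety planning vs standard | No change, b = 0 | b = 0.25 | b = 0.5 | All lost have events |
|---|---|---|---|---|
| 8 vs 4 | -16.7 | -13.3 | -10.0 | -3.3 |
| 9 vs 3 | -18.3 | -13.3 | -8.3 | +1.7 |
| 3 vs 9 | -8.3 | -13.3 | -18.3 | -28.3 |

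For 9 vs 3 at b = 0: (21 x 1/6)/30 = 11.7% and (27 x 1/3)/30 = 30.0%, which gives -18.3. No change minus imputation is 0.3(b - 1/6) - 0.1(b - 1/3) = 0.2b - 0.0167. The rule therefore favours safety planning more than imputation only when b is below 0.0167/0.2 = 8.3%.

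**Whole youths, 6 lost per arm (Newcombe 95% interval, Fisher p).**

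- Completers, 4/24 vs 7/24: -12.5 (-35 to +11), p = 0.49.
- No change, no earlier events, 4/30 vs 7/30: -10 (-29 to +10), p = 0.51.
- All lost have events, 10/30 vs 13/30: -10 (-32 to +14), p = 0.60.
- Only lost safety-planning youth have events, 10/30 vs 7/30: +10 (-13 to +31), p = 0.57.

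**The case against.** Several points against the concern stand.

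- **Event-free coding.** A reader might infer that it biases the comparison toward safety planning. At equal loss it does not, because the earlier-event share cancels. With more loss in standard practice and no earlier events, it moves the estimate against safety planning (3 vs 9 lost: -8.3 against -16.7).
- **Worse outcomes in the lost.** A reader might infer that the rule never tests these in safety-planning youth. It does so moderately: in the 15% vs 30% case it equals an arm-specific odds ratio of 2.4, double the completer rate. What it leaves out is anything harsher.
- **Ideation.** At equal loss and similar baseline values among the lost, the same shrinkage factor applies to ideation. The difference between outcomes lies in the value held and in what happens under unequal loss.
- **Reversal.** This needs stacked assumptions: loss near 20%, few earlier events, and an event in every lost safety-planning youth. In the illustration with lost standard-practice youth held at their earlier status, +8 falls to zero once 40% of the lost had an earlier event (32 - 24 - 20 x 0.4 = 0).
- **Coding.** The plan defines no binary attempts/NSSI endpoint, so every percentage here is conditional on any-event scoring.

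The reply that treatment failure simply means an event does not rescue the rule. The sentence itself defines failure as no change. Even if all the lost were coded as events, equal loss would give the same shrunken difference. The planned differential-attrition test would flag unequal loss but would not show how far the estimate depends on it.

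**Conclusion.** The point holds in limited form and is worth considering. For attempts/NSSI the plan's two descriptions of a lost youth conflict, and the single sensitivity analysis is not extreme. At equal loss with similar histories it keeps 80% of the completer difference at 20% loss and 93% at 2 lost per arm, whatever the event rates. With more loss in safety planning and almost no earlier events among the lost, it can agree exactly with imputation (8 vs 4 lost) or look better (9 vs 3), under the assumed rates of 1/6 vs 1/3. Agreement therefore does not show robustness to harsher outcomes in lost safety-planning youth.

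The documents do not support reading this as a threat to the pilot's main conclusions. Feasibility and acceptability are primary, effect estimation is disclaimed, and loss may be well under 20%. In the whole-youth illustration the estimate and interval move, while every coding stays non-significant. The treatment hypotheses are still to be tested on these outcomes, so the robustness statement should be worded to match what was tested.

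**What to change.** - **No change.** Keep it as one scenario, say whether the baseline or the last observed value is held, and drop the description of it as extreme.
- **Coding.** For attempts/NSSI, state whether the outcome is any event or a count, the SITBI recall window, and how a lost youth is scored.
- **Added analysis.** Run a delta-adjusted version of the planned multiple imputation for attempts/NSSI. Shift imputed outcomes toward worse in the safety-planning arm first, then in both arms, and report how the estimate and its confidence interval move. The shift must differ by arm to stress the comparison when loss is equal. If events are too few for a stable model, use an arm-specific worst case: an event in every lost safety-planning youth, with lost standard-practice youth following their completers.
- **CASA-based items.** For youth lost before 1 month, leave these to multiple imputation.

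The cost is SAP wording and modest programming on an imputation already planned, with no new data. The downside is a possibly less favourable robustness statement.
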